1.1. Synopsis

Title: Non-Invasive Brainstem Modulation for the Treatment of Non-motor symptoms in Parkinson’s Disease: A Randomized Controlled Trial (RCT) and an Open Label Extension (OLE) Study

1.1.1 Study Description

This paired set of studies seeks to establish the safety and efficacy of twice daily time-varying caloric vestibular stimulation (tvCVS) treatments using a solid-state Device developed by Scion NeuroStim, Inc (SNS), also known as ThermoNeuroModulation (TNM™), for treating symptoms associated with PD. The studies will be conducted at 15 centers, at minimum, in the United States and the United Kingdom. The majority of centers will be in the United States. Up to 290 participants will screen for the double-blinded, controlled, randomized clinical trial (RCT) and will self-administer tvCVS treatments twice daily in the home setting over a period of 12 weeks (84 days). Participants will continue to be enrolled in to the RCT until at least 184 participants have randomized prior to competitive enrollment closing. The RCT will be immediately followed by an open label extension (OLE) study during which all study participants will receive treatment for 12 weeks (84 days). Study participants will be followed for 16 weeks (112 days) post treatment-cessation and then the twice daily treatments will be re-introduced for the final 8 weeks (56 days). The RCT and OLE have been separated into two distinct studies with separate informed consent to enable the closeout and analysis of the RCT portion which will support regulatory submissions during the conduct of the OLE. However, participation in the OLE study will be a selection criterion for participating in the RCT, and thus, the two studies are defined within the context of a single protocol.

Please note that the terms treatment and therapy are used interchangeably within this protocol, as the TNM™ Device treatment is therapeutic.

1.1.2 Objectives

Randomized Clinical Trial (RCT): STEM-PD (SNS-PD-002)

Primary Objectives: The primary objective of the RCT will be to test the hypothesis that TNM™ treatments provide safe and effective therapy for the reduction of non-motor symptom burden in participants with PD.

Secondary Objectives: This study will seek to establish whether TNM™ treatments provide adjuvant therapeutic effectiveness beyond that observed with dopamine replacement therapies (DRTs) to (1) provide global benefits, (2) improve activities of daily living related to motor function, (3) provide clinically meaningful change (4) improve motor symptoms and (5) improve quality of life (QoL) for participants with PD.

Safety Objectives: This study will seek to establish the safety of TNM™ by monitoring adverse events by evaluating whether TNM™ is associated with a worsening of balance, functional

mobility and gait in participants with PD.

Exploratory Objectives: This study will seek to establish the effectiveness of TNM™ therapy for treating specific non-motor symptoms (NMS) and in treating motor complications from oral dopamine replacement therapies. Outcomes will evaluate the clinical meaningfulness of symptomatic improvements, explore the temporal kinetics of motor symptom response to treatment, evaluate the potential of Device therapy to improve gait and to establish the health economics for TNM™ therapy.

Open Label Extension OLE: STEM-PD-OLE (SNS-PD-003)

The purpose of the OLE study is to gather the additional data needed to support reimbursement.

Objectives: The OLE has been designed to address the following objectives: (1) demonstrate reproducibility of the results from the RCT in a second cohort (i.e. all participants, including recipients of active treatment and recipients of passive treatment in the RCT will receive active treatment in OLE), (2) evaluate effectiveness of the Device treatments over an extended treatment interval, (3) collect additional data to support health economic benefits, (4) confirm clinical meaningfulness of RCT results and (5) evaluate the potential for the device to slow disease progression.

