7.8.2. Primary Endpoint and Comparison of Interest

The primary endpoint is the change in MDS-NMS total score at the end of treatment. The primary comparison is its change in MDS-NMS total score during the RCT treatment period (days 29-113) versus the change in MDS-NMS total score during the OLE treatment period 1 (days 113-197). This analysis of the primary comparison will only utilize the passive-active treatment group. The analysis will utilize data obtained during the RCT as well as data obtained from the OLE baseline and the twelve weeks of the OLE in which the participants will have been given the intervention.

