7.8.2.1. Statistical Significance

The null hypothesis is that 12 weeks of active tvCVS treatments during the OLE will yield an equivalent change in the passive-active treatment group of NMS burden as that which occurred in response to passive treatment during the RCT. The alternative hypothesis is that the passive-active treatment group will demonstrate a greater reduction of NMS burden after 12 weeks of active tvCVS treatment during the OLE than occurred after 12 weeks of passive treatment during the RCT. Rejection of the null hypothesis will indicate that the intervention was successful. The threshold to determine statistical significance will be set at $\alpha = 0.05$ based upon a 1-tailed test.

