7.8.4. Secondary Endpoints

Multiplicity of study endpoints will be adjusted for using a hierarchical strategy whereby endpoints in the study are only considered to be statistically significant if both of the following are true: 1) p < 0.05 AND 2) the preceding endpoint was found to be statistically significant at the significance level $\alpha = 0.05$. More specifically, the hierarchical order for evaluation of efficacy endpoints is the following:

- 1. MDS-NMS Total Score (primary endpoint);
- 2. Combined measure of MDS-UPDRS Parts I, II, and III (sum score)
- 3. MDS-UPDRS Part II (secondary endpoint);
- 4. Overall CGI-I (secondary endpoint);
- 5. MDS-UPDRS Part III (secondary endpoint);
- 6. PDQ-39SI (secondary endpoint).

Note that all secondary endpoints have an *a priori* direction, thus, one-tailed tests will be utilized for analyses.

Secondary endpoint analysis will be conducted using the passive-active treatment group for the primary comparison of interest.

Analyses of the secondary endpoints will be conducted in a manner consistent with the primary endpoint except where noted.

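### The OLE primary test shares its comparator data with the RCT primary test, so its p-value is not independent confirmation of the RCT

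*Protocol*

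**What the plan says.** Protocol 1.1.2 lists as the first OLE objective to "demonstrate reproducibility of the results from the RCT in a second cohort". The parenthesis that follows makes clear that the cohort is the RCT participants themselves, from both arms. The same section says: "The purpose of the OLE study is to gather the additional data needed to support reimbursement".

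OLE SAP 7.8.2 narrows the test: "The primary comparison is its change in MDS-NMS total score during the RCT treatment period (days 29-113) versus the change" over OLE treatment period 1 (days 113-197). It adds: "This analysis of the primary comparison will only utilize the passive-active treatment group. The analysis will utilize data obtained during the RCT". OLE SAP 7.4 takes the RCT end-of-treatment score as the OLE baseline.

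On success, OLE SAP 7.8.2.1 sets a one-tailed 0.05 threshold and says: "Rejection of the null hypothesis will indicate that the intervention was successful". OLE SAP 7.8.2.2 likewise calls the endpoint successful on OLE significance alone. The hierarchy in OLE SAP 7.8.4 requires that "the preceding endpoint was found to be statistically significant at the significance level" of 0.05, but its first step is the OLE's own MDS-NMS test. The RCT result is not a step in it.

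The RCT SAP (Appendix 1 of the OLE SAP), sections 7.7.1 and 7.7.1.1, tests the active-arm MDS-NMS change to day 113 against the passive-arm change, also at one-tailed 0.05.

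**The concern.** A reader told that RCT results were reproduced in a second cohort will take the second result as fresh evidence. Here the passive arm's change to day 113 is subtracted in both tests. If the passive arm scores poorly at day 113 by chance, the RCT difference moves towards the device. The OLE contrast moves the same way for two reasons: the passive change looks worse, and the active change starts from a worse score. The two results can therefore agree by chance more often than two separate studies would.

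The OLE is meant to support reimbursement and clinical adoption (OLE SAP 2.1), and those are the readers for whom an apparent replication carries weight. As written, the OLE SAP would also let the intervention be called successful on the open-label result whatever the blinded comparison showed.

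**Working it through.** **Inputs from the documents.** 83 completers per RCT arm, SD 5.32 and difference 2.64 on MDS-UPDRS Part I (RCT SAP 4); 74 in the passive-active group, with the same SD and difference (OLE SAP 4); one-tailed 0.05 for each primary. The correlation between visits is not given and has to be assumed.

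**The plan's own figures.**
- RCT: 2.64 / (5.32 × √(2/83)) = 3.20, and Φ(3.20 − 1.96) = 89.2%, as stated.
- OLE paired t-test: noncentrality (2.64/5.32) × √74 = 4.27, giving 98.8% two-sided; the plan states more than 98%.

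**Structure.** Let A and P be the RCT active-arm and passive-arm changes, and O the OLE change in the former passive arm. The RCT statistic is mean(A) − mean(P). The OLE statistic is mean(O − P), with O − P = Y197 − 2·Y113 + baseline. I treat the OLE test as a paired contrast, as the plan's sample-size section does, rather than fitting the full MMRM.

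**Correlation of the two statistics.** Give A, P and O equal SD σ, and let ρ be the within-person correlation of P and O. Then:
- variance of the RCT statistic = 2σ²/83
- variance of the OLE statistic = 2σ²(1 − ρ)/74
- covariance = σ²(1 − ρ)/83
- correlation = ½ × √(1 − ρ) × √(74/83), where √(74/83) = 0.944

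The chance of two false positives is the bivariate normal probability that both statistics exceed 1.645. Dividing by 0.05 gives the chance of a positive OLE after a false-positive RCT.

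| ρ (assumed) | Correlation | Both falsely positive | OLE positive given false-positive RCT | At least one |
|---|---|---|---|---|
| −0.5 | 0.578 | 1.47% | 29.5% | 8.5% |
| −0.25 | 0.528 | 1.31% | 26.1% | 8.7% |
| 0 | 0.472 | 1.14% | 22.7% | 8.9% |
| +0.5 | 0.334 | 0.79% | 15.7% | 9.2% |
| Independent study | 0 | 0.25% | 5% | 9.75% |

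**Which ρ is plausible.**
- Equal visit variances with compound symmetry and a day-29 baseline give ρ = −0.5 whatever the visit correlation, because P and O share day 113 with opposite signs.
- Working from visit scores, with compound symmetry or autoregressive decay (0.5, 0.7 or 0.85 per 84 days) and either baseline definition, the correlation of the statistics is 0.47 to 0.58 and the conditional probability 23 to 30%. With the plan's own baselines (mean of days 0 and 29 for the RCT, day 29 for the OLE) and compound symmetry they are 0.556 and 28%.
- OLE SAP 4 uses 5.32 as the SD of the paired difference, the same value as the within-group SD in RCT SAP 4. Setting 2σ²(1 − ρ) = σ² gives ρ = +0.5, the 15.7% row.

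**Simulation check.** 40,000 null trials with independent visit errors and the baseline averaged over days 0 and 29 gave correlation 0.58, conditional probability 30%, at least one false positive 8.6%, and about 5% for each test alone.

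**Baseline adjustment.** OLE SAP 7.7.1 adds baseline as a covariate if the RCT and OLE baselines differ at 0.05, without giving the form. If it enters as the within-person baseline difference (an assumption), simulation under the same visit patterns puts the conditional probability at about 11 to 15%. That is lower, but still above 5%.

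**The case against.** The strongest reply is that the documents hide nothing and that these are separate studies. "The RCT and OLE have been separated into two distinct studies with separate informed consent": the RCT serves regulatory submissions and the OLE serves reimbursement. The second-cohort wording appears in the protocol synopsis, is followed by its own definition, and is absent from the OLE SAP objectives. The former passive arm's response to active treatment is also new data from people who had not had it before.

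Much of this stands, and it rules out three stronger readings that a reader might infer.

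- **That the protocol has an inflated family-wise error rate.** Two distinct studies with different uses do not normally share alpha. The 8.5 to 9.2% chance of at least one false positive is in fact below the 1 − 0.95² = 9.75% for two independent tests. Separate alpha is not in itself an error.
- **That a chance RCT result will usually confirm itself.** At 16 to 30%, some 70 to 84% of false-positive RCTs would not be confirmed.
- **That the OLE test exceeds its own 5% level.** It does not, if there is no period or expectation effect.

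The reply leaves the replication wording unanswered. Openly reusing the RCT control data does not make the second result independent of the first, and the success statement in OLE SAP 7.8.2.1 is not limited to the OLE comparison.

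**Conclusion.** The point holds as a fault in what the OLE is said to show. Its primary test shares comparator data with the RCT primary, so agreement between them is weaker evidence than the reproducibility objective implies. After a false-positive RCT, the OLE would also be positive about 16 to 30% of the time, roughly three to six times the 5% of an independent study.

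This rests on the global null, equal variances, the planned numbers (83 per arm and 74), and assumed visit correlations. The lower end takes the OLE SD of 5.32 at face value. The range leaves out the conditional baseline covariate, which may reduce it. The RCT primary analysis is unaffected.

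**What to change.** 1. In Protocol 1.1.2, replace the reproducibility objective with a statement that the OLE estimates the response of the former passive arm after switching to active treatment. Add there and in the OLE SAP (2.1 or 7.8.2) that the comparator is the same RCT passive-arm data, and that the p-value is supportive and not independent confirmation of the RCT.
2. In OLE SAP 7.8.2.1 and 7.8.2.2, limit the word successful to the OLE within-person comparison. Report it beside the RCT primary result, and do not present it as a stand-alone efficacy conclusion if the RCT primary is not met.
3. Optional: make the RCT primary the first gate of the OLE hierarchy in 7.8.4. This brings the chance of any false success to 5% but does not remove the dependence, so it cannot replace items 1 and 2.

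The cost of items 1 and 2 is wording only, with no new data, visits or analyses. The sponsor gives up the replication label and a free-standing OLE success claim after a failed RCT.

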1.1.3 Endpoints

All endpoints in the RCT will compare differences in change scores between the end of treatment visit and the baseline across the two treatment groups unless otherwise noted. In the OLE, the end of the 12-week (84 day) treatment period will be considered the primary timepoint for evaluating effectiveness of treatment. The measures outlined below will be used for both the RCT and the OLE (except where noted).

The primary endpoint will be the change in The International Parkinson and Movement Disorder Society Nonmotor Rating Scale (MDS-NMS) ¹ total score.

Secondary endpoints will include changes to the following scores:

- The International Parkinson and Movement Disorder Society Unified Parkinson's Disease Rating Scale Part II: Motor Aspects of Experiences of Daily Living (MDS-UPDRS II) ²
- The combined measure of The International Parkinson and Movement Disorder Society Unified Parkinson's Disease Rating Scale: Parts I, II and III³
- the Clinical Global Impressions Scale- Improvement (CGI-I)
- The International Parkinson and Movement Disorder Society Unified Parkinson's Disease Rating Scale Part III: Motor Exam (MDS-UPDRS III) ²
- the Parkinson's Disease Questionnaire 39 summary index score (PDQ-39SI) ⁴

Adverse events (AEs) will be monitored. A safety endpoint will assess whether device therapy negatively impacts balance, functional mobility or gait for participants with PD and will be measured via the mini-BESTest ⁵.

Exploratory endpoints will include the following:

- The Montreal Cognitive Assessment (MoCA)
- The Oral Symbol Digit Modality Test (oSDMT)
- The Modified Schwab and England Activities of Daily Living Scale (S&E)
- The Parkinson’s Sleep Scale-2 (PDSS-2)
- The Epworth Sleepiness Scale (ESS)
- The Functional Assessment of Chronic Illness Therapy-Fatigue Scale (FACIT-F)
- The Geriatric Depression Scale (GDS)
- The Parkinson’s Anxiety Scale (PAS)
- The Patient Reported Outcome – Parkinson’s Disease (PRO-PD)
- The MDS-NMS Non-Motor Fluctuations (NMF) Total Score
- The Hoehn & Yahr score
- Zarit Burden Interview
- The Unified Parkinson’s Disease Rating Scale Part I (UPDRS I)
- Encephalog™ Finger Tapping Test
- Encephalog™ Timed Up and Go Test (TUG) - 3-meter TUG at home and 10-meter TUG in the clinic
- Patient Global Impression of Improvement (PGI-I)– OLE only
- International Parkinson and Movement Disorder Society Sponsored Unified Parkinson’s Disease Rating Scale Part I: Non-Motor Aspects of Experiences of Daily Living (MDS-UPDRS I)

Treatment adherence, TNM™ Device usability/satisfaction and itemized answers from UPDRS IV will also be evaluated. A Non-Motor Symptom focused Clinical Global Impression of Improvement (NMS-CGI-I) and a transition question evaluating impression of change for NMS will also be used to help establish the clinical significance for the primary endpoint.

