3.4 Exploratory Endpoints

3.4.1 Objectives:

The exploratory endpoints of this trial have been selected to provide further support the primary and secondary endpoints of the study and to reveal the temporal kinetics of response to TNM™ therapy.

3.4.2 Endpoints:

- the Montreal Cognitive Assessment (MoCA) - rapid screening instrument for mild cognitive dysfunction in patients with neurologic disorders including PD (3 different versions [8.1, 8.2, and 8.3] will be used to avoid learning effects)
- the Oral Symbol Digit Modality Test (oSDMT) – quickly screens for organic cerebral dysfunction by measuring processing speed
- the Modified Schwab and England Activities of Daily Living Scale (S & E) ^{57 58 58 58 58} - clinical outcome assessment of an individual's ability to function in activities of daily living
- the Parkinson's Sleep Scale-2 (PDSS-2)- assessment to quantify nocturnal sleep issue in PD
- the Epworth Sleepiness Scale (ESS) – a brief measure that is commonly used to assess daytime sleepiness in PD and other disorders
- the Functional Assessment of Chronic Illness Therapy-Fatigue Scale (FACIT-F) - a measure of an individual's level of fatigue during their usual daily activities over the past week
- the Geriatric Depression Scale-15 (GDS-15) – a short questionnaire for assessing depression in older adults
- the Parkinson Anxiety Scale (PAS) – a brief questionnaire to detect anxiety severity in PD

- the Patient Reported Outcome – Parkinson’s Disease (PRO-PD) – a self-rating tool to assess PD symptom severity
- the MDS-NMS Non-Motor Fluctuations (NMF) Total Score - a rater completed assessment evaluating fluctuations of NMS in PD
- the Hoehn & Yahr score – staging tool describing the level of disability in PD (subcomponent of the MDS-UPDRS III)
- Zarit Burden Interview - measure of caregiving burden completed by caregivers
- Unified Parkinson’s Disease Rating Scale Part I (UPDRS I): a measure of mentation, behavior and mood in PD
- Finger tapping test – smart phone application (Encephalog™) providing a quantitative measure of bradykinesia
- Timed Up and Go Tests – smart phone application tests that measures gait and the probability of falls in adults (Encephalog™)
 - 3-meter TUG (time to complete)
 - 10-meter TUG (stride length, cadence, rotation time, time to complete)

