7. STATISTICAL METHODS

7.1. GENERAL METHODS

Descriptive statistical methods will be used to summarize the data from this study, with formal hypothesis testing performed for the primary and key secondary efficacy endpoints. Unless stated

otherwise, the term "descriptive statistics" refers to number of participants, mean, median, standard deviation, minimum, and maximum for continuous data, and frequencies and percentages for categorical data. For categorical variables, the denominator of percentages will be the number of subjects in the treatment group, except for those collected by study visit and/or scheduled time point, in which case the denominator of percentages will be the number of subjects with a non-missing value at the visit and/or the scheduled time point.

All data collected during the study will be included in data listings. Unless otherwise noted, the data will be sorted first by RCT treatment group, subject number, and then by date within each subject number.

All statistical testing will be two-sided and will be performed using a significance (alpha) level of 0.05 unless otherwise specified. P-values will be presented to three decimal places. For exploratory endpoints, inferential analyses including 95% confidence intervals and p-values will be provided, and no statements about statistical significance will be made. The p-values will be provided as informational only.

The statistical analyses may be conducted with the SAS® software package version 9.4 or higher or with GraphPad Prism software version 9.3.1 or higher.

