7.4. DEFINITIONS

Study groups: The group/cohort that originally received passive treatment during the RCT will be referred to as the passive-active group. The group/cohort that originally received active tvCVS treatment during the RCT will be referred to as the active-active group.

Study day: The study day will be calculated in reference to the date of the first baseline virtual visit during the RCT (Day 0). Although the informed consent for the OLE will be completed on day 113, plus or minus window days, because the RCT and OLE are part of the same protocol and the evaluation of effectiveness in the OLE depends on RCT data, all dates in this OLE SAP will be in reference to the first RCT visit (Day 0) as is specified in the protocol.

Analysis day: The analysis day will be calculated in reference to the date of the last assessment in RCT/first assessment in OLE (Day 113). Analysis day will be utilized for comparisons for passive-active participants.

OLE Baseline value: Values obtained at the End of Treatment (EOT) visit for the RCT will define the OLE baseline values. Values obtained at the most recent visit during the RCT will define the OLE baseline values in cases where data is missing for the EOT visit for the RCT.

Adherence (%): Adherence is defined as the total number of times subjects used the device in a given treatment period divided by twice the number of days the subject participated in that treatment period, multiplied by 100 to give a percentage.

Duration of Follow-up: The duration of follow-up will be defined as the number of days from the OLE Baseline until the End of Treatment period 2 (day 365) assessment or the last completed visit (phone call, virtual or in clinic).

Adverse Event:

Per protocol, an AE is any untoward medical occurrence, unintended disease or injury, or untoward clinical signs (including abnormal laboratory findings) in participants, users, or other persons, whether or not related to the investigational medical device. This definition includes events related to the investigational medical device and the events related to the procedures involved. For purposes of analyses, any AE specified on the Adverse Events eCRF page is considered an AE.

Adverse Device Effect (ADE):

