For the primary comparison of interest (i.e. passive-active group following 12 weeks of treatment), the least-squares mean differences with corresponding 95% confidence intervals and p values will be constructed using the MMRM model discussed previously. However, no regulatory claims will be made in relation to these outcomes. Therefore, no adjustments will be made to address multiplicity of endpoints.

Treatment adherence, the Patient Global Impression of Improvement (PGI-I) and itemized answers from both the TNMTM Useability Questionnaire and the UPDRS IV assessment tool for the passive-active group will be reported descriptively. To further explore the effects of treatment on individual NMS, effects of treatment on each of the individual MDS-NMS domains will be evaluated. These domains include the following: (1) Depression, (2) Anxiety, (3) Apathy, (4) Psychosis, (5) Impulse control and related disorders, (6) Cognition, (7) Orthostatic hypotension, (8) Urinary, (9) Sexual, (10) Gastrointestinal, (11) Sleep and wakefulness, (12) Pain, and (13) Other. Only participants that demonstrate burden in the specified domain will be evaluated. In practice, this means that if any participant shows no burden on a given MDS-NMS domain throughout the study, then they will be excluded from this exploratory analysis.

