7.9. EXPLORATORY ANALYSES

These exploratory endpoints have been added to support clinical applicability of the primary and secondary endpoints. They have been selected to provide additional details that will impact decisions made by prescribing physicians and reimbursement entities. Mean or median change with corresponding 95% confidence intervals and p values will be provided. No adjustments will be made to address a multiplicity of endpoints. Only participants who have

baseline data collected for the exploratory endpoints will be included in these efficacy analyses.

Only participants who have baseline data collected for the exploratory endpoints will be included in these efficacy analyses.

- 1. The Montreal Cognitive Assessment (MoCA): This endpoint will evaluate the change in MoCA score at the end of the treatment period (day 113) relative to the baseline (day 29). The MoCA collected at the study screen will be used to evaluate study eligibility only and will not be included in the analysis.
- 2. The Oral Symbol Digit Modality Test (oSDMT): This endpoint will evaluate the change in oSDMT score (total correct substitutions) at the end of the treatment period (day 113) relative to the baseline (day 29).
- 3. The Modified Schwab and England Activities of Daily Living Scale (S&E): This endpoint will evaluate the change in S&E score at the end of the treatment period (day 113) relative to the baseline (day 29).
- 4. The Parkinson's Disease Sleep Scale-2 (PDSS-2): This endpoint will evaluate the change in PDSS-2 score at the end of the treatment period (day 112) relative to the baseline (day 28).
- 5. The Epworth Sleepiness Scale (ESS): This endpoint will evaluate the change in ESS score at the end of the treatment period (day 112) relative to the baseline (day 28).
- 6. The Functional Assessment of Chronic Illness Therapy-Fatigue Scale (FACIT-F): This endpoint will evaluate the change in FACIT-F score at the end of the treatment period (day 112) relative to the baseline (day 28).
- 7. The Geriatric Depression Scale (GDS): This endpoint will evaluate the change in GDS score at the end of the treatment period (day 112) relative to the baseline (day 28).
- 8. The Parkinson's Anxiety Scale (PAS): This endpoint will evaluate the change in PAS score at the end of the treatment period (day 112) relative to the baseline (day 28).

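### In the OLE passive-active group, MoCA test form is fully confounded with treatment period, so the within-person MoCA contrast carries a form term of unknown size and direction

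*Protocol*

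**What the plan says.** Protocol 1.1.3 lists the MoCA first among the exploratory endpoints and says of its list of measures: "The measures outlined below will be used for both the RCT and the OLE (except where noted". Only the PGI-I is marked as OLE only. Protocol 3.4.2 explains the alternate forms: "3 different versions [8.1, 8.2, and 8.3] will be used to avoid learning effects".

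Protocol 4.1.1 and 4.1.2 assign the same form to every participant at each visit:

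| Visit | Form |
|---|---|
| Screening (day -14 to -1) | 8.1 |
| Baseline 2 (day 29) | 8.2 |
| RCT end of treatment (day 113) | 8.3 |
| OLE end of treatment 1 (day 197) | 8.1 |

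For the RCT, section 7.9 of the RCT SAP (Appendix 1 to the OLE SAP) defines the change: "This endpoint will evaluate the change in MoCA score at the end of the treatment period (day 113) relative to the baseline (day 29". The screening score stays out of the analysis: "The MoCA collected at the study screen will be used to evaluate study eligibility only".

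For the OLE, SAP 7.4 sets the baseline: "Values obtained at the End of Treatment (EOT) visit for the RCT will define the OLE baseline values". OLE SAP 7.8.2 defines the comparison for the primary endpoint as the change "during the RCT treatment period (days 29-113) versus the change in MDS-NMS total score during the OLE treatment period 1 (days 113-197", in the passive-active group only. OLE SAP 7.10 applies the same comparison to the exploratory endpoints, with the MoCA first: "For the primary comparison of interest (i.e. passive-active group following 12 weeks of treatment), the least-squares mean differences with corresponding 95% confidence intervals", together with p-values, from the MMRM. For exploratory endpoints OLE SAP 7.1 adds that "no statements about statistical significance will be made".

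**The concern.** Alternate forms protect against remembered answers. They do not guarantee equal difficulty. A between-arm comparison at the same visits does not need equal difficulty, because any form difference is common to both arms. A within-person comparison of two periods does need it. Here the passive period runs from form 8.2 to form 8.3 and the active period from form 8.3 to form 8.1, in that order for every participant. The day-113 form enters both changes, so it counts twice.

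No form term appears in the models of RCT SAP 7.7 or OLE SAP 7.8, and neither counterbalancing nor equating data are mentioned. A larger sample would not help, since it would only estimate the same mixture of device and form more precisely.

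At stake is the interpretation of the OLE MoCA estimate, its interval and its p-value. OLE SAP 7.10 says the exploratory endpoints were chosen to inform prescribers and reimbursement bodies, and Protocol 1.1.2 gives reimbursement support as the purpose of the OLE.

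**Working it through.** The documents state no figure for the MoCA contrast, so there is none to reproduce.

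**Inputs from the documents.** Forms by visit (Protocol 4.1.1 and 4.1.2); RCT change = day 113 minus day 29 (RCT SAP 7.9); OLE baseline = day 113 (OLE SAP 7.4); contrast = OLE change minus RCT change in the passive-active group (OLE SAP 7.8.2 and 7.10); expected group size 74 (OLE SAP 4).

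**Assumed inputs.** The form shifts f1, f2 and f3 (forms 8.1, 8.2 and 8.3) and the SD of the within-person contrast.

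**Form term with no device effect.**
- RCT change, passive group: f3 - f2
- OLE change: f1 - f3
- Contrast: (f1 - f3) - (f3 - f2) = f1 + f2 - 2*f3
- RCT active minus passive: (f3 - f2) - (f3 - f2) = 0

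Examples, in MoCA points (a positive contrast favours the device):

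| Assumed form difference | OLE contrast |
|---|---|
| 8.3 harder by 0.5 | +1.0 |
| 8.3 harder by 1 | +2.0 |
| 8.3 easier by 1 | -2.0 |
| 8.2 easier by 0.5 | +0.5 |
| 8.1 easier by 0.5 and 8.2 harder by 0.5 | 0 |

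A simulation with no device effect agreed. With form 8.3 harder by 0.5 the mean OLE contrast was 1.01, and the RCT difference stayed at about 0.01.

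**Chance of p < 0.05 from form alone.** For a paired t-test the non-centrality is sqrt(74) * shift / SD, with 73 degrees of freedom. For a net shift of 1 point:

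| Assumed contrast SD | Non-centrality | Two-sided p < 0.05 |
|---|---|---|
| 2 | 4.30 | 99% |
| 3 | 2.87 | 81% |
| 4 | 2.15 | 56% |
| 5 | 1.72 | 40% |
| 6 | 1.43 | 29% |

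A net shift of 0.5 point gives 29% at SD 3 and 11% at SD 6.

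To judge the SDs: with independent visit errors the contrast variance is (1 + 1 + 4) = 6 times the per-visit error variance. SDs of 2 to 6 thus correspond to per-visit noise of 0.8 to 2.4 points.

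**Baseline covariate.** OLE SAP 7.7.1 adds baseline as a covariate if the RCT and OLE baselines differ at p < 0.05. With slope b of change on baseline, the form term becomes f1 + (1 + b)*f2 - (2 + b)*f3. For an illustrative b = -0.5 this is f1 + 0.5*f2 - 1.5*f3. If form 8.3 is harder by 0.5, the shift falls from 1.0 to 0.75, and the rejection rate at SD 3 falls from 81% to 56%.

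**Re-exposure.** Form 8.1 is seen at screening and again at day 197, an interval of 197 + 1 = 198 to 197 + 14 = 211 days, about 28 to 30 weeks. Days 29 and 113 are first exposures to their forms.

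**The case against.** The strongest reply is that little hangs on this. The MoCA is outside the testing hierarchy (OLE SAP 7.8.4), its p-values are informational, and OLE SAP 7.10 rules out regulatory claims from it. The OLE is also open label with a single arm, so period, order and expectation are confounded with treatment for every OLE endpoint. All of that stands, and it keeps the point minor. It does not make the estimate interpretable: the exploratory label deals with multiplicity, not with a systematic shift in an avoidable component.

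The illustrated rates rest on assumed values, which is also true. Several stronger readings are tempting, and the documents do not support them:

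- **Any form difference becomes a device effect.** Only the net amount f1 + f2 - 2*f3 enters, and it can be zero with unequal forms.
- **The bias favours the device.** If form 8.3 is the easiest, it runs the other way and could hide a benefit.
- **Re-using form 8.1 inflates the active change.** A gain carried over 28 to 30 weeks may be small, and general test familiarity that levels off would raise the earlier, passive change more. The net sign is unknown.
- **The RCT result is affected too.** It is not, since both arms take the same form at each visit.

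**Conclusion.** The point holds for the OLE only. In the passive-active group, form and treatment period cannot be separated, and the planned MoCA contrast includes f1 + f2 - 2*f3. The coefficients 1, 1 and -2 apply to the unadjusted contrast in participants with a day-113 score. The conditional baseline covariate, or the OLE SAP 7.4 fallback to an earlier RCT value, changes the weights; the covariate would shrink the term in the illustration but not remove it.

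Size and direction cannot be found from the documents. A reader might take 81% as the false-positive rate of this endpoint. It is one cell of an illustration that needs a net 1-point shift and a contrast SD of 3, and the same shift gives 29% at SD 6. What does not depend on those assumptions is that the reported interval and p-value cannot tell a device effect from a form effect. The consequence is a possibly misleading exploratory estimate. No primary or hierarchical test is affected.

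**What to change.** **If forms can still be assigned,** rotate the whole sequence across participants, screening included, balanced within arm, and put form sequence in the model:

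| Sequence | Screening | Day 29 | Day 113 | Day 197 | Form term |
|---|---|---|---|---|---|
| A | 8.1 | 8.2 | 8.3 | 8.1 | f1 + f2 - 2*f3 |
| B | 8.2 | 8.3 | 8.1 | 8.2 | f2 + f3 - 2*f1 |
| C | 8.3 | 8.1 | 8.2 | 8.3 | f3 + f1 - 2*f2 |

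The three terms sum to zero, so with equal numbers the expected form term is zero. The interval between repeats stays as it is now. Rotating days 29, 113 and 197 while leaving 8.1 at screening would be worse: about a third of participants would repeat 8.1 at the RCT baseline, 30 to 43 days after screening. The cost is a form-assignment list for sites, a screening form (used for the MoCA eligibility cut-off) that varies between participants, and slight added noise in the RCT comparison if sequence is not modelled. Rotation does not remove re-exposure at day 197.

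**If forms have already been given,** amend OLE SAP 7.10 to report the within-person MoCA contrast descriptively without a p-value, to state that form and period are confounded, and to base any statement about cognition on the randomised RCT comparison. This costs a few sentences.

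The active-active versus passive-active difference during the OLE should not be used as the device effect. Forms cancel in it, but both groups are on active treatment, so it compares a second 12 weeks with a first.
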